## 3.1. Analysis Sets

Analysis sets define the subjects to be included in an analysis. Analysis sets and their definitions are provided in this section. The rules for inclusion of subjects in each analysis set will be determined before the study blind is broken for analysis. The analysis set will be identified and included as a subtitle of each table, figure, and listing.

# 3.1.1. All Randomized Analysis Set

The **All Randomized Analysis Set** will include all subjects who are randomized into the study. This is the primary analysis set for by-subject listings.

# 3.1.2. Full Analysis Set

The **Full Analysis Set (FAS)** will include all subjects who (1) are randomized into the study, (2) have received at least 1 dose of study drug, (3) are not HIV positive on Day 1 (defined as subjects with either a) negative Covance antibody test results at first post baseline assessment or b) negative local lab Day 1 rapid test), and (4) in order to contribute to the efficacy analyses of HIV infection, should have at least one post-baseline HIV laboratory assessment (from either local or central laboratory).

Of note, negative Covance antibody test results are defined as either (1) a negative HIV Screening antibody test result or (2) a positive Screening antibody test plus a negative discrimination antibody test result. Subjects will be grouped according to the treatment to which they were randomized.

The FAS is the primary analysis set for efficacy analyses.

## 3.1.3. Per Protocol Analysis Set

The **Per Protocol (PP) Analysis Set** will consist of all subjects in the FAS excluding those with any of the major protocol violations listed below. Subjects will be grouped according to the treatment they actually received. The PP analysis set will be used for an on study drug PrEP treatment (on-treatment) HIV infection sensitivity analyses of the primary endpoint.

PP analysis set will exclude (from FAS) subjects meeting any of the following criteria:

- Subjects where evidence suggests that they have pre-existing HIV that was contracted prior
  to first dose date of study drug (defined as subjects for whom HIV infection prior to first
  dose date of study drug cannot be excluded as the subjects did not have a Covance HIV
  antibody or HIV-1 RNA test analyzed between first dose date (inclusive) and prior to the
  date of diagnosis of HIV infection) based on Gilead's evaluation
- Subjects vaccinated for HIV (identified from the Medical History eCRF or Non-Study ARV Medication eCRF)
- Subjects who meet the exclusion criterion for receiving ongoing therapy with any of the medications listed in the table in protocol Section 5.4 including drugs not to be used with FTC and TAF

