## 1. INTRODUCTION

The primary analysis of HIV-1 pre-exposure prophylaxis (PrEP) in Study GS-US-412-2055 has been done (clinical study report [CSR] date: 25 March 2019) after all subjects had either a minimum follow-up of 48 weeks and at least 50% of the subjects had 96 weeks of follow-up after randomization or prematurely discontinued from the study. This statistical analysis plan (SAP) describes the statistical analysis methods and data presentations to be used in tables, figures, and listings (TFLs) of the end of blinded phase analysis, which will be performed when all subjects have either completed the end of blinded treatment visit or prematurely discontinued from the study. The end of blinded phase is also the end of randomized phase, and we will use the phrases double-blinded (DB) phase and randomized phase interchangeably. Although the study was unblinded for the primary analysis, blind was maintained at the participant, investigator and operational staff at Gilead.

This SAP is based on the study protocol amendment 5 dated 5 September 2018, the electronic case report form (eCRF), data transfers for laboratory tests, the Computer-Assisted Self-Interview (CASI) questionnaire, and dual energy x-ray absorptiometry (DXA). The SAP will be finalized before database finalization for the final unblinding of the end of blinded phase analysis.

[figure not shown]

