Last Dose Date (OLE phase) is defined as the latest of the OLE phase study drug end dates recorded on the "Extension Phase" Study Drug Administration eCRF with "Permanently Withdrawn" box checked for subjects who prematurely discontinued study drug according to the "Extension Phase" Study Drug Completion eCRF. This date will only be available for subjects treated in the OLE phase of the study. If the last dose date is missing for subjects who prematurely discontinued study drug in the OLE phase of the study, the latest of nonmissing OLE phase study drug start dates and end dates, the clinical visit dates, and the laboratory visit dates, excluding the date of 30-day follow-up visit, from the OLE phase data, will be used to impute the OLE phase last dose date.

**Last Study Date** is the latest of the randomized or OLE phase (if available) study drug start dates and end dates, the clinic visit dates, and the laboratory visit dates, including the 30-day follow-up visit date, for subjects who prematurely discontinued study or who completed study according to the Study Completion eCRF.

Last At-Risk of HIV Infection Date (DB phase) is (1) the date of HIV infection diagnosis as defined in Section 6.2.2 for subjects who have been diagnosed as infected with HIV during the DB phase or (2) the date of the last post-baseline HIV laboratory test (either local rapid or Covance HIV laboratory tests, including the 30-day follow-up visit date) during the DB phase for subjects who have not been infected with HIV during the DB phase.

Last At-Risk of HIV Infection Date (OLE phase) is (1) the date of HIV infection diagnosis as defined in Section 6.2.2 for subjects who have been diagnosed as infected with HIV during the OLE phase or (2) the date of the last post-baseline HIV laboratory test (either local rapid or Covance HIV laboratory tests, including the 30-day follow-up visit date) during the OLE phase for subjects who have not been infected with HIV.

**Baseline value** is defined as the last value obtained on or prior to Study Day 1 for each phase for all assessments, except for DXA BMD. The baseline value for DXA BMD is defined as the last value obtained on or prior to Study Day 14 of each phase.

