### 6.2.6. Sensitivity Analyses of the Secondary Efficacy Endpoint While On-Treatment (HIV Infection Rate Ratio Method)

A sensitivity analysis of the secondary endpoint will be based on HIV infections occurring while subjects are on-treatment during the double-blinded phase of the study using the PP analysis set. This on-treatment analysis will include HIV infection events and follow-up times occurring between first dose date to DB phase last dose date plus 10 days (for F/TDF) or plus 16 days (for F/TAF) and exclude:

- 1) HIV-1 infection events and follow-up time during the OLE phase.
- 2) Off study drug PrEP (off-treatment) HIV infection events and follow-up time defined as events and follow-up time occurring greater than 10 days for (F/TDF) or 16 days (for F/TAF) after permanent discontinuation of study drug (Appendix 7).
- 3) HIV infections and follow-up time occurring after subjects initiated any non-study PrEP treatment that includes the period after permanent discontinuation of study drug (including commercial drugs like Truvada®, generic Truvada, or investigational drugs like cabotegravir for PrEP with a stop date that is either ongoing or after permanent discontinuation of study drug).

The HIV infection incidence rate per 100 person-years of follow-up will be computed as the number of subjects with on-treatment HIV infection divided by the sum of all subjects' years (where a year is 365.25 days) of on-treatment follow-up while at risk of HIV infection in study. The duration of on-treatment follow-up while at risk of HIV infection is defined as the time between Day 1 (first dose date) and the end date (end date Day 1 date +1) where end date is defined as:

- For subjects who have been diagnosed as infected with HIV while on-treatment: the date of the on-treatment HIV infection which will be the date of the HIV infection diagnosis (as defined in Section 6.2.2).
- 2) For subjects who have not been infected with HIV while on-treatment, the earlier of:
  - a) last dose date + 10 days for F/TDF or + 16 days for F/TAF for subjects who permanently discontinued study drug (including subjects with off-treatment HIV infection)
  - date of last post-baseline HIV laboratory test (either local or Covance HIV laboratory tests, which may include the 30-day follow-up visit date) for subjects who have not permanently discontinued study drug

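### The per-protocol rule removes only early-diagnosed infections while everyone else's early person-time stays, so absolute PP rates read up to about 4% low

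*SAP*

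**What the plan says.** The exclusion in SAP 3.1.3 turns on the absence of a Covance "antibody or HIV-1 RNA test analyzed between first dose date (inclusive) and prior to the" diagnosis date. It closes with a judgement clause: "date of diagnosis of HIV infection) based on Gilead's evaluation". Its purpose is limited: "The PP analysis set will be used for an on study drug PrEP treatment (on-treatment) HIV infection sensitivity analyses".

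SAP 6.2.6 takes on-treatment follow-up as "defined as the time between Day 1 (first dose date) and the end date" for every PP participant. There is no delayed entry.

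The Schedule of Assessments in SAP 1.2 and the procedures table in Protocol Appendix 2 place central antibody/antigen testing at Screening, Week 4 and later visits. Day 1 has the on-site rapid test, with HIV-1 RNA only for participants with symptoms of acute infection.

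The SAP does not treat rapid tests uniformly. FAS membership can rest on a "negative local lab Day 1 rapid test" (SAP 3.1.2). Local tests are accepted for the endpoint (6.2.2) and for the end of at-risk time (3.8.1, 6.2.3). Appendix 12, item 16(d), says the FAS and PP populations use Covance or rapid-test results. The criterion in 3.1.3 names central tests only.

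Appendix Table 5 sets the absolute PP on-treatment rate in each arm beside the HIV incidence predicted without PrEP.

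**The concern.** The exclusion is conditioned on the outcome. An infection first detected at or before the first on-study central test leaves the numerator. The person-time over the same interval from all uninfected participants, and from those infected later, stays in the denominator. In that interval almost no infection can count.

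What is at stake is the absolute PP rate. In Appendix Table 5 a rate that reads low makes the comparison with predicted no-PrEP incidence look slightly better than it should.

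There is also a problem of definition. Take a participant with a negative Week 4 rapid test, a missing Week 4 central sample and a diagnosis at Week 12. Under 3.1.3 this person is excluded as possibly infected before dosing. Under Appendix 12, item 16(d), the rapid result could be counted. Two programmers could build different PP sets.

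**Working it through.** **Inputs.** From SAP 1.3.1: 2500 per arm, 1.44 infections per 100 person-years (PY) in both arms, average follow-up 2 years, margin 1.62, two-sided 5%. From SAP Table 3-1: Week 4 is nominal day 28 with window limit day 56, and Week 12 is day 84. The ±2-day visit window (Protocol 6.3) makes day 26 the earliest Week 4 visit. From SAP Appendix 8: 4250 PY per arm as an alternative person-time. Assumption: constant hazard at the planning rate.

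**The plan's own figure.** Expected events per arm = 0.0144 × 5000 = 72. SE of the log rate ratio = √(2/72) = 0.1667. Power = Φ(ln 1.62 / 0.1667 − 1.96) = 82.5%, which reproduces the stated minimum of 82%.

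**Effect of the rule, first central test at day d = 28.**
- Early person-time per arm = 2500 × 28 / 365.25 = 191.6 PY.
- Infections removed, at most = 0.0144 × 191.6 = 2.76 of 72.
- PP rate as written = (72 − 2.76) / 5000 = 1.385 per 100 PY, a fall of 2.76/72 = 3.8%. The removed participants' own person-time, about 0.1 PY, is negligible.
- PP rate with everyone entering at day 28 = 69.24 / (5000 − 191.6) = 1.44 per 100 PY. Delayed entry removes the bias.

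**Range, 5000 PY per arm.**

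| First central test | Infections removed | PP rate per 100 PY | Change |
|---|---|---|---|
| Day 26 | 2.56 | 1.389 | −3.6% |
| Day 28 | 2.76 | 1.385 | −3.8% |
| Day 56 | 5.52 | 1.330 | −7.7% |
| Day 84 | 8.28 | 1.275 | −11.5% |

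With 4250 PY per arm the change is −4.5% at day 28 and −9.0% at day 56. Each row applies the same first-test day to everyone.

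**Rate ratio.** The rule is the same in both arms, so the factor cancels. In a simulation of 3000 trials (d = 28, 2 years, true ratio 1), the mean log rate ratio was 0.001 under the PP rule and 0.001 with all infections kept. The mean PP rate was 1.385, and 1.441 with delayed entry. Losing 2.76 events per arm lowers power from 82.5% to 81.0%. If by chance only one arm lost 2.76 events, a ratio of 1.00 would become 69.24/72 = 0.96.

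**The case against.** The strongest defence is that the rule answers a real problem. A Day 1 rapid test, possibly antibody only, cannot rule out very recent infection. Some removed infections will have preceded the first dose, and removing them corrects an upward error. That stands, and it is one reason why the figures above are upper bounds. It justifies the screen; it does not justify keeping everyone else's person-time from the screened interval.

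The practical weight is also small. "The FAS is the primary analysis set for efficacy analyses", the FAS has no such exclusion, and Appendix Table 5 prints an FAS row beside each PP row. A shift of 1.44 − 1.385 = 0.055 per 100 PY is minor against the lower prediction limit of 2.51 that Appendix Table 8 gives at a rectal gonorrhea incidence of 15 per 100 PY. All of this stands.

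A reader might infer more than the documents support:
- **That each removed infection moves a PP rate by 10%.** This would take the 10 cases per arm in Appendix 9 (DBS 1.5) as an event forecast. They are an illustrative number for case-control power. On the planning figure of 72 events, one infection is 1/72 = 1.4%.
- **That the understatement is about 12%.** This needs essentially everyone to miss the Week 4 central test.
- **That negative rapid tests are ignored outright.** The criterion in 3.1.3 reads that way, but Appendix 12 points the other way and the evaluation clause leaves room. The documents leave this unsettled.
- **That genuine failures in poor adherers are being discarded.** Nothing in the documents shows how many participants have rapid results without central ones, or how well they adhered.
- **That exclusions were decided with knowledge of treatment.** SAP 1 says: "Although the study was unblinded for the primary analysis, blind was maintained at the participant, investigator and operational staff at Gilead". SAP 3.1 requires inclusion rules to be set before the blind is broken for analysis. Enrollment ended in June 2017 and the primary report is dated March 2019, so infections found at Week 4 or 12 long preceded it. What remains is that no one is named as making the evaluation blind to treatment.

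**Conclusion.** The point holds as a small downward bias in absolute PP on-treatment rates, together with an inconsistency about rapid tests. At the planning rate the bias is at most about 4% with an on-time Week 4 test and about 8% if the first central test is at day 56. It does not bias the rate ratio in expectation, and it leaves the FAS analysis untouched.

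The size rests on a constant hazard at 1.44 per 100 PY, on every removed infection being a true on-study infection, and on detection at the first central test after acquisition. An infection acquired just before Week 4 may test negative then, be diagnosed later and be kept, so the true effect should be smaller. The documents give no count of removed infections. This is a minor but worthwhile correction.

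**What to change.** In the PP on-treatment analysis, start at-risk time for every participant at the first negative HIV test after Day 1, and drop events and person-time before that test for all. The qualifying test should be a central antibody or RNA test, with a stated rule on whether a post-Day 1 negative rapid test qualifies when the central sample is missing. The Day 1 rapid test must not qualify. A confirmed positive rapid test on Day 1 bars entry (Protocol 6.2.2), so counting the negative one would leave the clock at Day 1 and remove the screen for pre-existing infection.

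Reconcile SAP 3.1.3 with Appendix 12, item 16(d). Replace the open sponsor evaluation with a programmed rule or a review blinded to treatment. If the primary analysis used the present definition (its SAP is a separate document), the result under that definition can be shown alongside for continuity.

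The cost is about 4% of PP person-time (191.6/5000 = 3.8%), a few sentences of SAP text and reprogramming of one sensitivity analysis.

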# 3.1.4. Safety Analysis Set

The **Safety Analysis Set** will include all subjects who (1) are randomized into the study and (2) have received at least 1 dose of study drug.

Subjects will be grouped according to the treatment they actually received. This is the primary analysis set for safety analyses.

## 3.1.5. DXA Analysis Sets

# 3.1.5.1. Hip DXA Analysis Set

The **Hip DXA Analysis Set** will include all subjects who (1) are in the Safety Analysis Set and (2) have nonmissing baseline hip BMD values. Subjects will be grouped according to the treatment they actually received.

# 3.1.5.2. Spine DXA Analysis Set

The **Spine DXA Analysis Set** will include all subjects who (1) are in the Safety Analysis Set and (2) have nonmissing baseline spine BMD values. Subjects will be grouped according to the treatment they actually received.

## 3.1.6. Pharmacokinetic Cohort Analysis Set

The **PK Cohort Analysis Set** will include all subjects who (1) are in the Safety Analysis Set, (2) are selected in the random sampling of 10% of the enrolled subjects as described in Section 1.2, and (3) have at least 1 nonmissing plasma PK, PBMC PK or DBS concentration value for any analyte of interest reported by the PK lab. The PK Cohort Analysis Set will be used for general PK analyses for the cohort substudy.

# 3.1.7. Pharmacokinetic Case-Control Analysis Set

The **PK Case-Control Analysis Set** will include all subjects who (1) are in the Safety Analysis Set, (2) have HIV infection or were selected as a matched control for a HIV infected subject, and (3) have at least 1 nonmissing plasma PK, PBMC PK or DBS concentration value for any analyte of interest reported by the PK lab. The PK Case-Control Analysis Set will be used for general PK analyses for the case-control substudy.

## 3.2. Subject Grouping

For analyses based on the All Randomized Analysis Set or the FAS, subjects will be grouped according to the treatment to which they were randomized. For other analyses, subjects will be grouped by actual treatment received. The actual treatment received will differ from the randomized treatment only when the actual treatment received differs from randomized treatment for the entire treatment duration.

#### 3.3. Strata and Covariates

This study does not use a stratified randomization schedule when enrolling subjects. Analyses of BMD, renal safety endpoints, weight and BMI will be adjusted for baseline F/TDF for PrEP.

### 3.4. Examination of Subject Subgroups

## 3.4.1. Subject Subgroups for Efficacy Analyses

The HIV infection rate per 100 PY will be analyzed for the following subject subgroups (see Section 6.2.7 for details):

- Age (years): (a) < 25 and (b)  $\ge 25$
- Race: (a) any black (includes mixed races with any black ancestry) and (b) nonblack
- Ethnicity: (a) Hispanic and (b) Non-Hispanic
- Region: (a) US and (b) Ex-US (Canada and European Union)
- Region: (a) North America (US/Canada) and (b) European Union
- Baseline F/TDF for PrEP medications (a) Yes and (b) No (defined in Section 7.6.3)
- Screening HIV risk characteristics, from CASI screening questionnaire
- Highest level of education: (a) < 4 year college (ie. Less than high school, High school/GED, Some college, 2-year college/AA, Other) and (b) ≥ 4 year college (ie. 4-year college, Master's degree, Doctoral degree, Professional degree)
- Circumcised: (a) Yes and (b) No
- Recreational drug use in the last 3 months prior to Screening: (a) Yes and (b) No
- URAI partners in the last 90 days prior to Screening: (a) ≤ 3 URAI partners and
   (b) > 3 URAI partners
- Screening HIV risk characteristics, from AUDIT screening questionnaire
- Six or more drinks on one occasion (a) Never or frequency of alcohol use never and (b) Yes (includes Less than monthly, Monthly, Weekly, Daily or almost daily)
- Any history of rectal gonorrhea, rectal chlamydia or syphilis STI in the past 24 weeks from Medical History eCRF: (a) Yes and (b) No

# 3.4.2. Subject Subgroups for Safety Analyses

Selected bone safety endpoints may be analyzed for the following subject subgroups (see Section 7.3.1.1 for details):

• Baseline F/TDF for PrEP medications (a) Yes and (b) No (defined in Section 7.6.3)

Selected renal safety endpoints may be analyzed for the following subject subgroups (see Sections 7.4.3.1 and 7.4.5.1 for details):

• Baseline F/TDF for PrEP medications (a) Yes and (b) No (defined in Section 7.6.3)

Selected renal biomarker ratios and fasting metabolic assessments may be analyzed for the following subject subgroups (see Sections 7.4.1.1 and 7.4.2.1 and 7.2.3.1 for details):

• Baseline F/TDF for PrEP medications (a) Yes and (b) No (defined in Section 7.6.3)

# 3.5. Multiple Comparisons

The noninferiority evaluation of the incidence of HIV infection per 100 PY when all subjects have a minimum follow-up of 48 weeks and at least 50% of the subjects have 96 weeks of follow-up after randomization is the prespecified primary comparison. However, 3 interim IDMC analyses prior to the analysis for the primary endpoint have been planned with an alpha penalty of 0.00001 for each interim IDMC meeting. Therefore, the alpha level for the primary endpoint was adjusted to 0.04997 (corresponding to 95.003% confidence interval [CI]) using the FAS. No alpha level adjustment is applied for the analysis at the end of blinded phase.

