8.4.2. Secondary Efficacy Analysis

A similar analysis to the primary analysis, when all participants have 96 weeks of follow up after randomization will be conducted. Similar incidence rates and CIs will be reported for the extended follow up time.

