8.6. Statistical Testing Procedure

The primary hypothesis of non-inferiority of F/TAF relative to F/TDF, with respect to the incidence of HIV-1 infection rate per 100 PY will be tested first. Non-inferiority test will be performed at one-sided, 0.025 alpha level. Multiplicity adjustments for safety endpoints will be performed at Week 48 of the blinded phase with a fallback procedure {[Wiens 2005](#)} in the sequential order given below with pre-specified two-sided alpha levels:

- a) Hip BMD ($\alpha = 0.02$)
- b) Spine BMD ($\alpha = 0.01$)
- c) Renal biomarkers ($\alpha = 0.02$)

CCI

CCI

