8.8. Sample Size

A sample size of 2500 in each arm (1:1 randomization) provides at least 82% power to show F/TAF is non-inferior to F/TDF with respect to the HIV-1 infection rate. In this power analysis, a HIV-1 infection rate of 1.44 per 100 PY in the F/TAF and F/TDF treatment arms, a 2-sided Type 1 error rate of 5%, a non-inferiority margin of 1.62, and an average follow up of 2 years are assumed.

The non-inferiority margin of 1.62 and HIV-1 infection rate of 1.44 per 100 PY are based on an equal weighting approach using 3 historical studies of F/TDF versus placebo/untreated arms in MSM populations that are very similar to the population intended for this study (see [Table 8-1](#) below; the NI margin of 1.62 per 100 PY is the square-root of the lower bound of the 95% CI (2.64) of rate ratio to preserve 50% of treatment effect). The largest of the 3 studies is the IPREX study and the unprotected receptive anal intercourse (URAI) subgroup of the IPREX study is a high-risk population similar to the intended population of this study. Equal weighting for the 3 studies gives relatively more weight to the 2 smaller contemporary studies (PROUD and IPERGAY) than the alternative method of inverse variance weighting, thus providing an

estimate that is likely to be closer to the true estimate of F/TDF efficacy for PrEP. PROUD and IPERGAY were conducted when F/TDF was already established as an effective PrEP medication and represent the status for participants in the proposed study. IPREX, the largest and earliest of these 3 studies, was conducted when the effectiveness of F/TDF for PrEP was not established; thus, patients were informed of the unproven efficacy of F/TDF, which likely contributed to the much lower adherence rate in the IPREX trial. In contrast, PROUD and IPERGAY are more recent studies and were conducted after F/TDF was approved for prevention of HIV in a similar risk population, and likely contributed to the much higher adherence rate reported.

Table 8-1. Efficacy Information from Truvada as PrEP in MSMs

Clinical Trial	Sample Size Placebo (PY Follow-Up)	Sample Size F/TDF (PY Follow-Up)	HIV Infections (Incidence per 100 PY [95% CI])		Rate Ratios in HIV Infection Rates, per 100 PY [95% CI]	Enrollment
			PBO	F/TDF		
IPREX (URAI subgroup) at screening	753 (1054)	732 (1055)	56 (5.3) [4.0, 6.8]	23 (2.2) [1.4, 3.2]	2.4 [1.5, 3.9]	July 10, 2007 - Dec 17, 2009

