## 6.2.5. Primary Analysis of the Secondary Efficacy Endpoint (HIV Infection Rate Ratio Method)

The analysis purpose of the secondary efficacy endpoint is to assess the noninferiority of treatment with F/TAF relative to treatment with F/TDF via HIV infection rate ratio estimation from a Poisson regression model. Noninferiority will be assessed using a 95% CI constructed using a generalized model associated with a Poisson distribution and logarithmic link with the treatment group being the main effect and a noninferiority margin of 1.62.

It will be concluded that F/TAF is noninferior to F/TDF if the upper bound of the 2-sided 95% CI of the rate ratio (F/TAF group over F/TDF group) of the HIV infection incidence rate is less than 1.62 (Appendix 2).

If noninferiority of F/TAF versus F/TDF is established, the same 95% CI used in evaluating noninferiority will be used to evaluate superiority. If the upper bound of the 95% CI is less than 1, then superiority of F/TAF over F/TDF using the rate ratio estimation is established. The p-value from a Poisson model will also be used to assess superiority as a secondary assessment. The FAS will be used for the secondary efficacy endpoint analysis and the superiority evaluation.

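### SAP 6.2.5 allows a second formal non-inferiority or superiority conclusion on HIV infection after the primary comparison has used all the alpha; it should be labelled supportive.

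*SAP*

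**What the plan says.** **Primary comparison.** Protocol 8.6 tests non-inferiority first: "Non-inferiority test will be performed at one-sided, 0.025 alpha level". SAP 3.5 deducts "an alpha penalty of 0.00001 for each interim IDMC meeting" for three meetings, so that "the alpha level for the primary endpoint was adjusted to 0.04997 (corresponding to 95.003% confidence interval [CI]) using the FAS". SAP 1 and 6 record that this analysis has already been carried out and reported.

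**End of the blinded phase.** On the later analysis SAP 3.5 says only: "No alpha level adjustment is applied for the analysis at the end of blinded phase". SAP 6.2.4 sets a null hypothesis at the same rate ratio of 1.62. SAP 6.2.5 gives the decision rule, "It will be concluded that F/TAF is noninferior to F/TDF if the upper bound of the 2-sided 95% CI of the rate ratio" lies below 1.62. If the same interval lies wholly below 1, "then superiority of F/TAF over F/TDF using the rate ratio estimation is established". Neither rule is conditional on what the primary analysis showed.

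**Protocol status of the later endpoint.** Protocol 8.1.3 places HIV incidence at 96 weeks of follow-up for all participants under other secondary endpoints, not in the ordered alpha-controlled list. Protocol 8.6 assigns it no alpha. Protocol 8.4.2 calls for an analysis similar to the primary one and adds: "Similar incidence rates and CIs will be reported for the extended follow up time".

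**Confidence level.** SAP 6.2.5 uses 95%. The table shell for this analysis (SAP Appendix 2, Appendix Table 2) shows a 95.003% CI, and the SAS code in SAP Appendix 12 sets alpha=0.04997.

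**The concern.** The two analyses use the same trial, rate ratio and margin, and the second contains all the data of the first. A decision rule worded as a conclusion gives any claim missed at the primary a second, correlated chance at the full 5%, although nothing remains of the 0.05.

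Superiority is where this matters most. Testing superiority after non-inferiority on the same interval protects the error rate within one analysis, not across two. Had the primary shown non-inferiority but not superiority, SAP 6.2.5 would still allow superiority to be declared established from the later cut.

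**Working it through.** **1. The plan's own alpha.** 0.05 − 3 × 0.00001 = 0.04997, and 100 × (1 − 0.04997) = 95.003. Both SAP 3.5 figures reproduce. One-sided, the primary is run at 0.04997 / 2 = 0.024985. Adding the three penalties back gives exactly 0.05, so nothing remains.

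**2. Check of the model.** Protocol 8.8 assumes 1.44 per 100 PY, 2500 per arm and 2 years on average, which is 0.0144 × 2500 × 2 = 72 events per arm. The standard error of the log rate ratio is √(2/72) = 0.1667. Power is Φ(ln 1.62 / 0.1667 − 1.96) = Φ(0.935) = 82.5%, matching the stated 82%. The normal approximation for the log rate ratio is therefore a fair basis for what follows.

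**3. Chance of a false claim at either analysis.** Let t be the person-years at the primary divided by those at the end of the blinded phase. At the null boundary the two test statistics are standard normal with correlation √t. The critical values are c₁ = 1.9602 (one-sided 0.024985) and c₂ = 1.9600 (one-sided 0.025). Then

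P(either) = 1 − Φ₂(c₁, c₂; √t).

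| t | P(either), one-sided | Excess over the primary's 2.4985%, points |
|---|---|---|
| 0.70 | 3.78% | 1.3 |
| 0.75 | 3.67% | 1.2 |
| 0.80 | 3.54% | 1.0 |
| 0.85 | 3.40% | 0.9 |
| 0.90 | 3.24% | 0.7 |
| 0.95 | 3.02% | 0.5 |

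The excess is the probability that the primary fails and the later analysis succeeds. Two independent tests would give 4.94%, which is the ceiling.

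**4. Why t runs from 0.70 to 0.95.** This range is an assumption.
- Primary: SAP Appendix 8 gives 4250 PY per arm as the estimate for the primary analysis. It is a planning figure for the comparison with historical placebo, so only a proxy here.
- End of the blinded phase: no figure is given. SAP Appendix 3 has 5387 treated participants, or 2693.5 per arm, and 96 weeks is 1.84 years. SAP Appendix 9 dates enrolment from September 2016 to June 2017, so I allowed 0 to 4.5 months (0.375 years) of extra average follow-up.
- Longest case, full retention: 2693.5 × (1.84 + 0.375) ≈ 5966 PY, so t ≈ 0.71.
- Short case, no extra follow-up and 90% of person-time retained: 2693.5 × 1.84 × 0.9 ≈ 4460 PY, so t ≈ 0.95.

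Lower retention in the short case would put the final total below 4250 PY, which is impossible for cumulative data, so those combinations were dropped.

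**5. Check by simulation.** I simulated Poisson counts at 1.44 per 100 PY in the F/TDF arm, with 4250 PY per arm at the primary and Wald intervals on the log rate ratio.

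| Final PY per arm | t | Non-inferiority null (ratio 1.62), either analysis | Superiority null (ratio 1), either analysis |
|---|---|---|---|
| 5000 | 0.85 | 3.45% | 3.3% |
| 6000 | 0.71 | 3.8% | 3.7% |

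The primary alone gave about 2.5% and 2.4% under the two nulls.

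**6. Would a gate on primary non-inferiority be enough?** For a repeat of the non-inferiority claim, yes, because a gated repeat adds no error. For superiority, no. In the same simulation at a true ratio of 1, allowing late superiority only after primary non-inferiority left the either-analysis rate unchanged at 3.3% and 3.7%. A later interval wholly below 1 goes with a primary interval below 1.62 in practically every trial. Only a gate on primary superiority, or supportive status, closes that route.

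**The case against.** There is a good case for the plan, and much of it stands.

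- **Level of the primary test.** A reader might infer that the stated 2.5% is breached. The documents do not support that. The 0.025 in Protocol 8.6 and the 0.04997 in SAP 3.5 are set for the primary comparison, which keeps its level whatever is done later. Neither document promises 2.5% across both analyses.
- **Fidelity to the protocol.** A reader might also infer that the SAP invents a test where the protocol wanted only description. Protocol 8.4.2 asks for an analysis similar to the primary one, and Protocol 8.4.1 contains both the 1.62 rule and the superiority rule. Repeating the model, the interval and the comparison with 1.62 and 1 is within the protocol. What the protocol does not supply is alpha for a second formal conclusion.
- **Disclosure.** SAP 3.5 says openly that the later analysis is unadjusted, and SAP 6.2 calls the endpoint secondary throughout. Nominal testing of such endpoints is common. But SAP 6.2.5 nowhere calls the result nominal or supportive, and its verbs are those of a confirmatory test.
- **Conditional harm.** The excess needs a claim to fail first and succeed later. Neither document gives the primary result, so no actual claim can be said to be affected. If non-inferiority was shown at the primary, restating it costs nothing.

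**Conclusion.** The point holds as one about the inferential status of the later analysis. The 0.05 is fully used at the primary, yet SAP 6.2.5 attaches ungated formal conclusions to a later, overlapping analysis of an endpoint outside the alpha-controlled set. Across the two analyses the one-sided chance of a false claim is about 3.0% to 3.8%, which is 0.5 to 1.3 points above the primary alone. This rests on the assumed information fraction of 0.95 to 0.70 and on the normal approximation, which simulation supports.

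It would be wrong to go further and say that the primary result is compromised or that the later analysis should not be run. The practical exposure is a superiority claim first declared at the end of the blinded phase, against which non-inferiority at the primary gives no protection. The mismatch between 95% and 95.003% has a negligible numerical effect, but the text, shell and code should agree.

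**What to change.** Keep the analysis that Protocol 8.4.2 calls for: same Poisson model, rate ratio, interval, and comparison with 1.62 and 1. Change only its status.

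- **SAP 3.5:** add that the end-of-blinded-phase HIV analysis is nominal and supportive, and that formal non-inferiority and superiority conclusions rest on the primary analysis alone.
- **SAP 6.2.5:** replace the concluding and establishing language with a statement that the rate ratio and its nominal CI are reported and described as consistent or not with the primary result. Present the superiority p-value as nominal. Make the hypotheses in 6.2.4 read accordingly.
- **Confidence level:** use one level in SAP 6.2.5, Appendix Table 2 and the Appendix 12 code. For a nominal analysis 95% is the natural choice.

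Sharing alpha between the two analyses is no longer possible, because the primary was already run at a one-sided 0.024985. An equal split would have needed about 1.62% each at t = 0.70, rising to 2.06% at t = 0.95.

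The cost is SAP wording, one table shell and one line of code. The real downside is that no formal claim, superiority in particular, can be made from the later data cut.
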